5. NON-COMPARATIVE INTERIM ANALYSIS

The RCT and the OLE have been designed as two portions of a single protocol with separate informed consents. This design will allow for closeout of the RCT and analysis of study data while the OLE is ongoing. However, it is possible that non-comparative, blinded interim analyses may be needed to support the Sponsor's activities, while the RCT is ongoing. As such, non-comparative analyses may be performed to evaluate the percent change in the coefficient of variation between

² Protocol version 5.0 expanded eligibility criterion by lowering the MDS-UPDRS Part I threshold to 9 or more. Given this change, the standard deviation of the MDS-NMS for the total sample is estimated to be lower than 70.8 points calculated for participants with MDS-UPDRS Part I scores of 10 or more.

baseline and post treatment for the primary and secondary outcome measures using the full study cohort (i.e., pooled data from both active and passive treatment arms; allocation to remain blinded) that have both baseline and end of treatment data available. This metric provides a measure of confidence that statistical significance for a given endpoint will be achieved. This metric would be used for the purpose of fundraising. If interim analyses are performed, the results will be shared with the Independent Medical Monitor (IMM; see section 6) and Safety Medical Monitor, but results will not be shared with study site staff, investigators or Sponsor (Scion NeuroStim) staff directly involved in the trial. Results suggesting futility may be taken into consideration in the IMM recommendation to proceed or pause the study, but results indicating high probability for efficacy will not be considered as an early stopping criterion for the study. Because this non-comparative interim analysis, if performed, will be non-comparative with blinding of data unequivocally maintained and the results will not be shared with individuals who can influence the outcome of the study, the results do not pose any difficulty in terms of Type I error control or bias (Administration_CDRH 2016). Therefore, no adjustments will be made to the alpha level for evaluating the primary or secondary endpoints using this non-comparative approach.

The interim analysis utilizes as its metric the ratio of the sample standard deviation divided by the sample mean. This metric is calculated at baseline and post treatment. The difference between these two values is divided by its baseline value as depicted in the following formula:

where:

 $\%\Delta_{SD/X}$ = the percent change in the coefficient of variation in the outcome (e.g., MDS-NMS total) score between baseline and post treatment which may be interpreted as the percent confidence that statistical significance of the outcome will be achieved in the study

 $X_{baseline}$ = the mean of the outcome scores at baseline – for outcomes collected at both baseline visits, the $X_{baseline}$ will be the mean of the study participants' baseline scores, BL_{ave}

 $SD_{baseline}$ = the standard deviation of the outcome scores at baseline – for outcomes collected at both baseline visits, the $SD_{baseline}$ will be the standard deviation of the study participants' BL_{ave} scores

 X_{post} = the mean of the outcome scores at the end of the treatment period

 SD_{post} = the standard deviation of the outcome scores at the end of treatment

For each noncomparative interim analysis, two cohorts may be evaluated. The first will be the cohort for which end of treatment data exist (i.e., data collected at either the end of the scheduled treatment period or an early termination visit). The second cohort will only evaluate data from participants that completed the visit at the end of the regularly scheduled treatment period and will exclude those with early termination from the study.

The figure below provides sample sizes that would be required to obtain percent confidence of meeting the primary endpoint assuming a change in the standard deviation of scores divided by the mean metric between the baseline and the end of treatment assessment.

[figure not shown]

Figure 1. Estimated percent confidence of achieving statistical significance in the primary endpoint according to pooled interim data collected from both treatment arms. Sample sizes that would be required to obtain percent confidence of meeting the primary endpoint assuming a change in the standard deviation of scores divided by the mean. For example, if a difference of 10% of the SD/x metric is observed in a sample of 50 participants, the metric would provide 80% confidence that the endpoint will be statistically significant at the end of the study.

CONFIDENTIAL-Page 11 of 66

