4. SAMPLE SIZE DETERMINATION

The sample size for this study was set to achieve ~ 90% power to detect a minimal clinically important difference (MCID) of -2.64 points in the MDS-UPDRS: Part I (Horvath, Aschermann et al. 2017) for both the RCT and the first treatment period during the OLE. This estimated group sample sizes of 83 and 83 (166 total) to complete the RCT (assuming 10% attrition) achieves 89.2% power to detect a difference of 2.64 points in the MDS-UPDRS Part I total score for the null hypothesis that both group average change scores are equal and the alternative hypothesis that the average change score of the active treatment group represents greater symptomatic improvement than that of the passive treatment group given an estimated within group standard deviation of 5.32 points and a 2-sided significance level (alpha) of 0.05.

This sample size also achieves > 90% power to evaluate the primary endpoint of the STEM-PD OLE (see the STEM-PD OLE SAP for additional details).

Note that the primary outcome measure for the STEM-PD RCT is the MDS-NMS, not the MDS-UPDRS: Part I. However, the two scales are highly correlated (correlation coefficients = 0.75-0.85) (Chaudhuri, Schrag et al. 2019, van Wamelen, Martinez-Martin et al. 2021), and the MDS-UPDRS Part I has a pre-established MCID whereas the MDS-NMS does not. Given the high correlation reported for these two outcome measures in previous studies, an analysis was performed to estimate the MCID for the MDS-NMS. The MCID for the MDS-UPDRS: Part I is

2.64 points (Horvath, Aschermann et al. 2017). Since the estimated standard deviation of the MDS-UPDRS Part I for this study is 5.32 points, the MCID represents 49.6% of the standard deviation.

The standard deviation of the MDS-NMS scale has been reported as 65.87 points (Chaudhuri 2020). Using the same proportion of the standard deviation, the estimated MCID for the MDS-NMS scale for this study would be 32.7 points. Additionally, in an unpublished study analysis of participants from the original validation study, Martinez-Martin determined that among a cohort with MDS-UPDRS Part I scores greater than 10, which approximates the inclusion criterion for this study, the standard deviation of the MDS-NMS was 70.8 points. Utilizing a definition of 49.6% of the standard deviation, based upon the Martinez-Martin study, the MCID for the MDS-NMS scale would be 35.1 points.

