Further, Norman et. al., 2003 (Norman, Sloan et al. 2003) suggested that the MCID be defined as 50% of the standard deviation. Using the standard deviation of 65.87, the MDS-NMS MCID would be 32.9 points. As noted above, however, the proposed study requires subjects to have an MDS-UPDRS Part I score of at least 9 at the study screen. Therefore, utilizing the standard deviation of 70.8 points (Martinez-Martin, *unpublished*), the MDS-NMS MCID would be 35.4 points². As such, the estimated MCID range for improvement in the MDS-NMS for this Statistical Analysis Plan is -32.7 to -35.4 points. While these values provide estimates for sample size calculations, the MCID for the MDS-NMS from data collected within this study using methodology described in section 7.6.1.3.

Notably, the sample size (184 to randomize), derived from the MDS-UPDRS Part I also achieves 85.7% power to detect the estimated MCID minimum of -32.7 and 92.8% power to detect the estimated MCID maximum of -35 points in the MDS-NMS.

Competitive enrollment will be used. Participants will continue to be enrolled until at least 184 are randomized in the RCT, and if there are additional participant withdrawals, they will not be replaced. Any participant who had entered the baseline period but had not yet randomized when the competitive enrollment target is achieved may be withdrawn from the study prior to randomization, and as a result, will not be included in any of the analyses. Data from all randomized study participants will be evaluated for analyses of safety and efficacy. The protocol has planned for up to 290 study participants to be screened. The sample size of 184 to randomize allows for attrition of 10% in the RCT as well as attrition of 10% in the first treatment period of the OLE while still maintaining adequate power to evaluate the primary endpoints of those studies.

[figure not shown]

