7.7.1. Primary Endpoint

The primary endpoint is the change in MDS-NMS total score at the end of the treatment period (day 113) relative to baseline (mean of day 0 and day 29) scores.

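### The blinded interim "percent confidence" of a significant result is computed from pooled SD/mean and interim n alone, so it cannot estimate the chance of significance

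*SAP*

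**What the plan says.** RCT SAP Section 5 provides for optional interim analyses on data pooled across both arms with allocation blinded. The metric is the percent change in SD/mean from baseline to end of treatment. Section 5 says: "This metric provides a measure of confidence that statistical significance for a given endpoint will be achieved". Its definition of the metric adds that it "may be interpreted as the percent confidence that statistical significance of the outcome will be achieved in the study". The Figure 1 legend gives a worked case: "if a difference of 10% of the SD/x metric is observed in a sample of 50 participants, the metric would provide 80% confidence" of a significant endpoint at the end of the study.

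Appendix 2 gives the conversion. A chi-square statistic is formed from the interim n and the two SD/mean values, a right-tailed probability p is taken on n − 1 degrees of freedom, and confidence is 1 − p. The tables are headed with an alpha of 0.05, which enters no step.

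Section 5 names two uses. "This metric would be used for the purpose of fundraising". Also: "Results suggesting futility may be taken into consideration in the IMM recommendation to proceed or pause the study". No futility threshold is given. A favourable reading is not a stopping criterion, and no alpha adjustment is made.

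**The concern.** The final primary test is a one-tailed comparison of active with passive (RCT SAP 7.7 and 7.7.1.1). Its chance of success depends on the arm difference, the variability of the change score, the final sample size and alpha. The interim metric uses none of these. Any shared movement of the two arms, such as a placebo response or regression to the mean, moves the reading without changing the arm difference.

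A second problem affects MDS-NMS. Change in the primary endpoint is taken "relative to baseline (mean of day 0 and day 29) scores", and Section 5 likewise computes the baseline SD from two-visit averages where both visits exist. An average of two visits has a smaller SD than a single visit, so setting it against a single-visit post-treatment SD raises the reading when nothing has changed.

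At stake are the soundness of a proceed-or-pause recommendation and of a success figure shown to funders.

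**Working it through.** **Inputs.** From the documents: the Appendix 2 steps and tables; n = 50 (Figure 1 example); MDS-NMS SD, "The standard deviation of the MDS-NMS scale has been reported as 65.87 points"; 83 completers per arm; a 35-point difference (Section 4); one-tailed alpha 0.05. Not in the documents, so assumed: baseline MDS-NMS mean 100–200, how each arm moves, how SD moves with the mean, and the between-visit correlation.

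**1. Reproduce the plan's figure.** Let r = (post SD/mean) ÷ (baseline SD/mean). Then χ² = (n − 1)/r². For n = 50 and a 10% rise, χ² = 49/1.1² = 40.4959. The printed p of 0.1988 is the left tail, giving 1 − 0.1988 = 80.12%, as tabulated. The 5% and 30% entries (65.81%, 98.98%) match in the same way. The right tail named in step 5 is 0.8012, which gives 1 − 0.8012 = 19.88%. The text of step 5 therefore contradicts the tables and the Figure 1 legend. The tables' convention is used below.

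**2. No change.** r = 1, so χ² = 49 and the reading is 47.3%. This needs no assumption about the data.

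**3. Label swap.** Exchanging the arms changes neither the pooled mean, the pooled SD nor n, so the reading is identical, while the one-tailed result reverses. This needs no numbers. A simulation illustrates it (4,000 trials per scenario, assumed baseline mean 150, SD 70.8, baseline-to-post correlation 0.5, first 50 at interim). With active down 32.7 points and passive unchanged, the median reading is 88.9% and 90% of trials are significant. With the arms exchanged, the median reading is 89.2% and 0% are significant.

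**4. Useless device, shared fall of 10% in the mean.** The true chance is about 5% throughout.
- SD constant: r = 1/0.9, reading 82.6%.
- SD falls 5%: r = 0.95/0.9, reading 67.6%.
- SD falls 10%: r = 1, reading 47.3%.

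**5. Working device, 35-point benefit.** The SAP states "92.8% power to detect the estimated MCID maximum of -35 points in the MDS-NMS". With SD 65.87 and 83 per arm, 35/(65.87 × √(2/83)) = 3.423, and Φ(3.423 − 1.960) = 92.8% (two-sided 0.05, normal approximation), matching that figure. With SD 65.87 constant in each arm, the pooled post-treatment SD is √(65.87² + 17.5²) = 68.16. The pooled mean is the baseline mean plus the average of the two shifts.

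| Active / passive shift | Mean 100 | 125 | 150 | 200 |
|---|---|---|---|---|
| 0 / +35 | 8.4% | 14.5% | 20.0% | 28.5% |
| −17.5 / +17.5 | 60.5% | 60.5% | 60.5% | 60.5% |
| −25 / +10 | 84.2% | 80.3% | 77.4% | 73.6% |
| −35 / 0 | 97.8% | 95.1% | 92.2% | 87.0% |

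The arm difference is 35 points in every row. Only the shared shift differs.

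**6. Two-visit baseline, nothing changed.** With equal visit SDs and correlation ρ, r = 1/√((1 + ρ)/2). The reading is 52.3%, 57.3%, 67.2% and 76.3% at ρ = 0.95, 0.9, 0.8 and 0.7, against 47.3% for a like-for-like comparison.

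**The case against.** The strongest reply is that little depends on this number. The analysis is optional and blinded, and a high reading cannot stop the trial. Results are kept from sites, investigators and sponsor staff directly involved, alpha is untouched, and the IMM is only permitted to consider a futility reading. All of that is correct, and it limits the seriousness of the point. It does not make the stated interpretation true.

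Several objections to the illustrations also have force. The tables cover only increases of 5% to 30%, so the 47% for no change and the 8–29% readings extend the formula beyond what is printed. However, the formula applies at those values, and a futility reading would have to come from small or negative changes. A 35-point worsening on passive in 12 weeks is an extreme case, and intermediate splits read 60–84%. The 83% for a useless device needs a constant SD; with SD falling up to 10% the range is 47–83%. The two-visit effect is small at a correlation of 0.95. The SAP does not name the SD behind its 92.8% power, although SD 65.87 reproduces it.

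These points narrow the examples but do not touch the label-swap argument. The metric would track the arm difference only if the passive arm did not change and within-arm SD stayed constant. The SAP states neither condition, and even then the reading would not be calibrated to the final test or sample size.

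**Conclusion.** The concern holds. The interim reading does not estimate the probability of a significant active-versus-passive result, and this follows from its construction without any assumed value. At n = 50 its neutral reading is 47%. A useless device can read 47–83% after a shared 10% fall in the mean, depending on how SD moves. A 35-point benefit can read from 8% to 98%, for baseline means of 100–200 and constant within-arm SD. Those ranges rest on the stated assumptions; the structural conclusion does not.

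The consequence is limited to the IMM's possible use for futility and to fundraising. Type I error and the final analysis are not affected. The right-tailed wording in step 5 is a separate, secondary error: followed literally, it turns the example's 80.1% into 19.9%.

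**What to change.** In RCT SAP Section 5, delete the statements that the metric expresses confidence or percent confidence of statistical significance. Delete Figure 1 and the Appendix 2 conversion and tables that support them. Delete the sentence that lets the IMM weigh this metric for futility. If pooled SD/mean is still to be reported, label it descriptive and uninformative about efficacy. If any Appendix 2 steps are kept, correct the tail in step 5 to agree with the tables.

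The cost is SAP wording only, with no change to data collection or to the primary analysis. The sponsor gives up an interim figure that does not measure the chance of success.

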1.3 Abbreviations

ADL: activity of daily living

AEs: adverse events

ANCOVA: analysis of covariance

BL_{ave}: average score from a given assessment from the two baseline assessments

BID: twice daily

CFR: Code of Federal Regulations

CGI-I: Clinical Global Impressions of Improvement Scale

CRA: Clinical Research Associate

C-SSRS: Columbia Suicide Severity Rating Scale

CVS: caloric vestibular stimulation

DRN: dorsal raphe nucleus

DRT: dopamine replacement therapy

ePROs: electronic patient reported outcomes

ESS: Epworth Sleepiness Scale

FDA: United States Food and Drug Administration

FACIT-F: Functional Assessment of Chronic Illness Therapy-Fatigue Scale

GCP: Good Clinical Practice

GDS: Geriatric Depression Scale

ICF: Informed Consent Form

ICH: International Conference on Harmonisation of Technical Requirements

ID: identification

IJLI: intrajejunal levodopa infusion

IRB: Institutional Review Board

ITT: intention-to-treat

LED: light emitting diode

MCID: minimal clinically important difference

MDS-NMS: International Parkinson and Movement Disorder Society Nonmotor Rating Scale

MDS-UPDRS I: International Parkinson and Movement Disorder Society Sponsored Unified Parkinson's Disease Rating Scale Part I: Non-Motor Aspects of Experiences of Daily Living

MDS-UPDRS II: International Parkinson and Movement Disorder Society Sponsored Unified

STEM-PD, V6.0 -- CONFIDENTIAL

Clinician version – not for patient use

Parkinson's Disease Rating Scale Part II: Motor Aspects of Experiences of Daily Living

MDS-UPDRS III: International Parkinson and Movement Disorder Society Sponsored Unified Parkinson's Disease Rating Scale Part III: Motor Exam

MDS-UPDRS: the International Parkinson and Movement Disorder Society Sponsored Unified Parkinson's Disease Rating Scale

MHRA: Medicines and Healthcare products Regulatory Agency

Mini-BESTest: mini-Balance Evaluation Systems test

MoCA: Montreal Cognitive Assessment

NMF: non-motor fluctuations

NMS: non-motor symptom

NMS-CGI-I: Non-Motor Symptom focused Clinical Global Impression of Improvement

NMSS: Non-Motor Symptom Scale

NSR: non-significant risk

OLE: open label extension

OLE SAP: the statistical analysis plan for analysis planned for the open label extension

oSDMT: oral Symbol Digit Modality Test

PAS: Parkinson's Anxiety Scale

PD: Parkinson's disease

PDQ-39SI: Parkinson's Disease Questionnaire 39 summary index score

PDSS-2: Parkinson's Disease Sleep Scale-2

PI: Pulsatility Index

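### The RCT interim metric compares two-visit baseline averages with a single end-of-treatment score, so with equal visit SDs it rises although nothing has changed in the patients

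*SAP*

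**What the plan says.** The RCT SAP (attached as Appendix 1 to the OLE SAP) allows optional pooled, blinded interim looks in section 5. The metric is "the ratio of the sample standard deviation divided by the sample mean", computed at baseline and after treatment, with the difference divided by the baseline value.

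- **Baseline side.** For any outcome taken at both baselines, SD_baseline "will be the standard deviation of the study participants", computed on their BL_ave scores. Protocol section 1.3 defines BL_ave as the "average score from a given assessment from the two baseline assessments".
- **Post-treatment side.** SD_post is "the standard deviation of the outcome scores at the end of treatment", which is one assessment.
- **Primary endpoint.** RCT SAP 7.7.1 takes the day-113 MDS-NMS change "relative to baseline (mean of day 0 and day 29) scores". MDS-UPDRS Part II and PDQ-39SI likewise use the mean of day 0 and day 28, against day 112 (7.7.2.1 and 7.7.2.4).
- **Conversion.** Appendix 2 of the RCT SAP turns a rise in SD/mean into percent confidence by a chi-square calculation. The Figure 1 legend gives the example "if a difference of 10% of the SD/x metric is observed in a sample of 50 participants, the metric would provide 80% confidence".
- **Use.** The stated purpose is fundraising. In addition, "Results suggesting futility may be taken into consideration in the IMM recommendation to proceed or pause the study".

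Neither section 5 nor Appendix 2 corrects for the averaging of two baseline assessments, and neither gives a test-retest correlation.

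**The concern.** Averaging two assessments removes part of the visit-to-visit noise, so the SD of the averages is smaller than the SD of one visit when the visits are equally variable. The mean is not reduced in the same way. SD/mean is therefore lower on the baseline side for a reason that has nothing to do with treatment, and it rises when the single end-of-treatment visit is set against it. Appendix 2 counts every such rise towards success.

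At stake is the accuracy of a figure shown to funders and to the IMM. A reading that starts too high flatters the prospects of the primary endpoint and can soften a futility signal. It also makes readings hard to compare between outcomes with averaged and single-visit baselines.

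**Working it through.** **1. Reproduce the plan's figure.** Appendix 2 sets chi-square = (n − 1) × (CV0/CV1)² on n − 1 degrees of freedom, where CV is SD/mean, and confidence = 1 − p. For n = 50 and a 10% rise, chi-square = 49/1.21 = 40.4959. The table prints p = 0.1988 and 80.1235%. That p is the left-tail probability, although step 5 of Appendix 2 calls it right-tailed. Followed literally, step 5 would give 19.9%. Nine table entries (n = 5, 50 and 75; rises of 5% to 30%) match the left-tail rule to four decimals. The tables and the Figure 1 example agree with each other, so that rule is used below.

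**2. Like-for-like reference.** With unchanged scores and one assessment on each side, CV1/CV0 = 1 and chi-square = n − 1. The confidence reads 47.3% at n = 50 and 47.8% at n = 75.

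**3. Effect of the averaging.** Suppose both baseline visits and the end-of-treatment visit have the same mean and SD, and the two baseline scores correlate at r. Then:

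- SD(BL_ave) = SD × sqrt((1 + r)/2)
- CV1/CV0 = sqrt(2/(1 + r)), which exceeds 1 for every r below 1
- chi-square = (n − 1)(1 + r)/2

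The documents give no r, so these values are assumed:

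| Assumed r | Rise in SD/mean | Chi-square, n = 50 | Confidence, n = 50 | Chi-square, n = 75 | Confidence, n = 75 |
|---|---|---|---|---|---|
| 0.9 | 2.6% | 46.55 | 57.3% | 70.3 | 60.0% |
| 0.8 | 5.4% | 44.10 | 67.2% | 66.6 | 71.7% |
| 0.7 | 8.5% | 41.65 | 76.3% | 62.9 | 81.8% |
| 0.6 | 11.8% | 39.20 | 84.0% | 59.2 | 89.5% |

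At r = 0.95 the rise is 1.3% and the n = 50 reading is 52.3%. The SAP's example of a 10% rise would arise from averaging alone at r = 2/1.21 − 1 = 0.65.

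**4. Sampling variation.** A simulation with no change in patients (n = 50, 20,000 runs, equicorrelated normal scores, CV 0.5) gives median readings of 57.3%, 67.1%, 76.4% and 84.1% for r = 0.9, 0.8, 0.7 and 0.6. The mean readings are lower: 55.9%, 62.9%, 68.9% and 74.2%. The chance of reading at least 80% is 31% at r = 0.8 and 56% at r = 0.6. With a single-visit baseline it is 16% and 24%.

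**5. Unequal baseline SDs.** Let the day-0 SD be k times the day-29 SD, with equal means and an end-of-treatment SD equal to the day-29 SD. Then SD(BL_ave) relative to day 29 is sqrt((k² + 1 + 2rk)/4).

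- r = 0.8, k = 1.1: sqrt((1.21 + 1 + 1.76)/4) = 0.996, so the rise almost vanishes.
- r = 0.8, k = 1.2: sqrt((1.44 + 1 + 1.92)/4) = 1.044, so the metric falls.
- r = 0.6, k = 1.1: sqrt((1.21 + 1 + 1.32)/4) = 0.939, so a rise of about 6% remains.

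**The case against.** The strongest objection is that the size rests on quantities the documents do not give. This stands. A reader might infer that the metric will report two-thirds confidence or more whenever nothing has changed. That needs n of about 50 or more and r of 0.8 or lower. At r = 0.9 or 0.95 and n = 50 the reading is only 57% or 52%. The equal-SD condition is also open, because Baseline 1 is a telemedicine visit and Baseline 2 is in clinic (Protocol 4.1.1).

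A second objection is that little depends on the figure. The look is optional, pooled and blinded, cannot stop the trial for efficacy, and has no futility threshold. This also stands. A reader might infer that the final test is compromised, but section 5 does not feed into the endpoint analysis and no alpha is spent.

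Third, a reader might take MDS-UPDRS Part III as clearly free of the problem. The schedule of events has Part III at both baselines, in a modified form on day 0, so section 5 read literally would average it. The exemption comes from the baseline definition in 7.3 and the endpoint text in 7.7.2.3. For the combined score it comes from 7.7.2.1, which uses days 28/29. There the case is firmer, because Part I is not scheduled at Baseline 1.

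Finally, one can say that a metric reading 47% for unchanged data is not a probability of success anyway. That is correct, and it is a separate weakness. It does not excuse comparing unlike quantities.

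**Conclusion.** The mismatch is in the written definitions. It affects MDS-NMS, MDS-UPDRS Part II and PDQ-39SI. With equal and unchanged visit means and SDs, its direction is upward for any r below 1. For an assumed r of 0.9 to 0.6, unchanged scores read about 57% to 84% at n = 50 and 60% to 90% at n = 75, against 47% to 48% like for like. These are plug-in values, and at n = 50 they match the simulated medians. Average readings are somewhat lower. A sufficiently larger SD on day 0 would cancel or reverse the effect.

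The consequence is limited to a possibly flattering fundraising figure and a weaker futility signal to the IMM. Part III and the combined score escape only if sections 7.3 and 7.7.2 are taken to override section 5, and section 5 does not say so.

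**What to change.** In RCT SAP section 5, define X_baseline and SD_baseline for every outcome from the single Baseline 2 score: day 29, or day 28 for the ePROs. One assessment is then compared with one assessment, and the wording for every outcome settles the Part III and combined-score question. RCT SAP 7.10.5 already plans a Baseline 2-only comparison for the primary outcome, so there is a precedent. For MDS-NMS the change also pairs an in-clinic baseline with the scheduled in-clinic day-113 visit. Early-termination assessments, which one interim cohort includes, may still be virtual (Protocol 7.2.1).

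The tail named in step 5 of Appendix 2 should be corrected at the same time to match the printed tables.

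The cost is a one-line change with no new data, and probably a less favourable reported figure. The change makes the two sides comparable. It does not turn the metric into a probability that the trial will succeed, and the report to the IMM should not present it as one.
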